4.3 Justification for Dose

Justification for 2 doses administration schedule

There are several published studies evaluating 2 or 3 administrations of attenuated RSV or parainfluenza virus type 3 (PIV3) candidate vaccines (4) (5) (8) (24) (25) (26) (27) (28) (29). Generally, there was a high level of restriction of the second administration, and limited serum immune responses. The main effect was vaccine infectivity in the individuals who did not respond to the first administration. Two administrations of RSV Δ NS2/ Δ 1313/I1314L may improve the infectivity of either dose.

Justification for vaccine dose

The vaccine dose has been selected based on benefit/risk assessment based on results obtained the first Phase I/II VAD00001 study conducted in infants and toddlers 6 to 18 months of age receiving 2 doses of RSVt vaccine at concentration of [REDACTED]

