4.2 Scientific Rationale for Study Design

Rationale for enrolling pediatric participants

It is expected that infants who already had RSV infection or who are seropositive present a lower virus shedding and thus a lower probability of vaccine virus transmission to their close contacts (23). In VAD00014 study, potential pediatric participants will not be screened based on their RSV baseline serostatus. Therefore, in order to maximize the probability of transmission during the study, enrolling a higher proportion of children aged 6 to 12 months may help to increase the proportion of seronegative participants and thereby increase the probability of transmission to pediatric participants receiving the placebo and / or to ad-hoc close contact participants. Some efforts will be made to enroll twins, to optimize the probability of transmission, and to limit the possible impact of age difference between the RSVt vaccine and placebo recipients. Stratification by age group could also be a way to control for the age distribution among RSVt vaccine and placebo recipients (eg, to ensure that for siblings, some younger and older children will receive RSVt vaccine).

Evaluation of Vaccine Virus Transmission

Transmission of the vaccine virus will be defined as presence of detected vaccine virus in the pediatric participants placebo-recipients and ad-hoc close contact participants, by RSVt qRT-PCR assay. Planned nasal swabs will be collected on all pediatric participants (ie, vaccinees and placebo recipients) on D01, D04, D08, D11, D15, D18, D22, D64, and D71. Nasal swabs will not be collected on D57 or D85 since vaccine virus shedding is not expected to last so long after the first administration and is expected to be lower after the second administration.

Based on an NIH study conducted with the same vaccine construct and on the same target population (20), it is expected that the probability of transmission from vaccinees to other persons will be higher when the virus shedding in the vaccinees is the highest (between 4 and 9 days after vaccine administration), so that nasal swabs will be collected regularly after the first administration to be able to detect vaccine virus. Vaccine virus shedding is expected to be lower after the second administration (8), justifying the collection of fewer nasal swabs after the second administration, and performing the interim analysis of the primary objective of transmission after the first dose.

[REDACTED]

Illness Visit(s)

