9.5 Sample Size Determination

No sample size calculation was done as there are no statistical hypotheses in this study. A total of 100 pediatric participants (ie, 50 per study intervention group) are planned to be enrolled, based on clinical feasibility.

10 Supporting Documentation and Operational Considerations

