#### 3.4.2.2 Vaccine virus shedding

Titer of vaccine virus shedding evaluated by RSVt qRT-PCR in nasal swabs after each vaccination will be summarized at each timepoint (D01, D04, D08, D11, D15, D18, D22, D64, and D71) in pediatric participants by study intervention group with 95% CIs:

- Number and percentage of participants with detected shedding ( $\geq$ LOD) at each timepoint
- Number and percentage of participants with quantified shedding ( $\geq$ LLOQ) at each timepoint

In addition, titer of vaccine virus shedding will be summarized using descriptive statistics as presented in [Table 3.1](#).

Viral shedding analyses will be performed on the SafAS.

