#### 4.2.3 Infectivity

Infectivity is defined as detection of vaccine virus strain in any post-vaccination nasal swab sample by RSVt qRT-PCR and/or a  $\geq$  4-fold rise from baseline (D01) in RSV A serum nAb titers and/or RSV serum anti-F IgG Ab titers.

- Infectivity after vaccination 1: Detection of vaccine virus shedding ( $\geq$  LOD) by RSVt qRT-PCR at any post-vaccination 1 NS samples (D04, D08, D11, D15, D18 and D22) and/or a  $\geq$  4-fold rise from baseline (D01) in RSV A serum nAb titers and/or RSV serum anti-F IgG Ab titers at D57
- Infectivity after vaccination 2: Detection of vaccine virus shedding ( $\geq$  LOD) by RSVt qRT-PCR at any post-vaccination 2 NS samples (D64 and D71) and/or a  $\geq$  4-fold rise from baseline (D01) in RSV A serum nAb titers and/or RSV serum anti-F IgG Ab titers at D85
- Infectivity after any vaccination: Detection of vaccine virus shedding ( $\geq$  LOD) by RSVt qRT-PCR at any post vaccination NS samples (D04, D08, D11, D15, D18, D22, D64 and D71) and/or a  $\geq$  4-fold rise from baseline (D01) in RSV A serum nAb titers and/or RSV serum anti-F IgG Ab titers at D57 and /or D85

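### No readable analysis separates dose-2 results by dose-1 take: arm-level D64/D71 detection dilutes shedding in children first infected by dose 2, and the dose-2 infectivity definition counts persisting dose-1 antibody

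*Protocol*

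**What the plan says.** Protocol 4.3 reviews published studies of two or three administrations of attenuated RSV or PIV3 candidates. It reports that the second administration was highly restricted and that "The main effect was vaccine infectivity in the individuals who did not respond to the first administration". Of the present construct it says only that two administrations "may improve the infectivity of either dose".

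Protocol 4.2 states: "Vaccine virus shedding is expected to be lower after the second administration (8), justifying the collection of fewer nasal swabs after the second administration". The schedule has six swabs after dose 1 (D04 to D22) and two after dose 2 (D64, D71).

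Under SAP 3.4.2.2, shedding "will be summarized at each timepoint (D01, D04, D08, D11, D15, D18, D22, D64, and D71) in pediatric participants by study intervention group", as the number and percentage detected and quantified, with descriptive statistics of titer from Table 3.1. SAP 3.4.5 adds a subgroup by age (below 12 months, 12 months and over). Shedding after each administration is a primary objective.

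SAP 4.2.3 defines infectivity after vaccination 1, after vaccination 2 and after any vaccination. The second definition begins "Infectivity after vaccination 2: Detection of vaccine virus shedding" and is also met by a rise of at least 4-fold at D85 in RSV A neutralizing or anti-F IgG titer. That rise is measured from D01. SAP 4.2.6.3 derives baseline RSV serostatus (naive, exposed, undetermined) from serum anti-F IgA.

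**The concern.** The protocol's own account of earlier studies locates the effect of a second dose in children the first dose missed. The readable analyses never isolate those children, although the SAP derives dose-1 infectivity for each child.

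For shedding, a low arm-level percentage at D64 and D71 fits two different situations: little shedding in anyone, or frequent shedding in the few children infected for the first time by dose 2. The study is meant to inform a large Phase III trial, for which the difference is worth knowing. The interim analyses stop at D22, so only the final analysis can show it.

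For infectivity, a reader would take the vaccination-2 row as the effect of dose 2. With D01 as its reference, that row can be largely a dose-1 result.

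**Working it through.** **The plan's own figure.** Protocol 9.5: "A total of 100 pediatric participants (ie, 50 per study intervention group) are planned to be enrolled, based on clinical feasibility". There is no power calculation to reproduce; 100 / 2 = 50 per arm.

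**Other inputs.**
- Earlier dose-1 data (Protocol 2.2): infectivity 100% in one study and 88% in another; a rise of at least 4-fold in neutralizing titer in 80% in the first. All come from seronegative children given the NIH formulation. Children here are not screened for serostatus (Protocol 4.2), so applying these figures to this trial is an assumption.
- Dose-2 detection: not given. Assumed 50% or 88% in missed children and 0% or 10% in dose-1 responders, rounded to whole children.
- Intervals: two-sided 95% Clopper-Pearson, as planned.

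**Step 1, shedding.** Arm percentage = (detected among missed + detected among responders) / 50. At 88% take, 44 responded and 50 − 44 = 6 were missed.

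| Missed children | Responders | Whole arm | Exact 95% CI, arm | Exact 95% CI, missed only |
|---|---|---|---|---|
| 3/6 (50%) | 0/44 | 3/50 = 6% | 1.3–16.5% | 11.8–88.2% |
| 5/6 (83%) | 0/44 | 5/50 = 10% | 3.3–21.8% | 35.9–99.6% |
| 3/6 (50%) | 4/44 | 7/50 = 14% | 5.8–26.7% | 11.8–88.2% |
| 5/6 (83%) | 4/44 | 9/50 = 18% | 8.6–31.4% | 35.9–99.6% |

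Sensitivity to take:
- 80% take, 10 missed: 50–90% in the missed children appears as 10–26% of the arm.
- 60% take, 20 missed: 50–90% appears as 20–42%.
- 100% take: there is no missed stratum.

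The same arm figure can also arise differently. With 100% take, 5/50 shedding among responders again gives 10% (3.3–21.8%), so the arm row cannot separate that from 5/6 in missed children.

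**Step 2, infectivity after vaccination 2.** Assume 88% take, 80% dose-1 seroresponse (0.80 × 50 = 40 children) and a share of those still at least 4-fold above D01 at D85. Count = 40 × persistence + takes among the 6 missed.

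| Persistence to D85 (assumed) | No dose-2 take in missed | 5/6 take in missed |
|---|---|---|
| 50% | 20/50 = 40% | 25/50 = 50% |
| 75% | 30/50 = 60% | 35/50 = 70% |
| 100% | 40/50 = 80% | 45/50 = 90% |

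Carry-over supplies 40 to 80 percentage points; nearly complete take in the missed children adds 10. The row is pushed up, and it responds more to antibody persistence than to dose 2.

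**Step 3, what the planned counts already yield.** After any vaccination is the union of the other two definitions. With complete data, n(any) − n(after vaccination 1) is therefore the number first meeting the definition after dose 2. In the example, (49 − 44) / (50 − 44) = 5/6. This gives a count, but no D64/D71 detection rate, titer or planned interval. It can also include children who qualify on serology alone, which wild-type RSV could cause.

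**The case against.** Several points against the concern have force.

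- **Not an objective.** The sentence in Protocol 4.3 describes other candidates, and the section gives a second rationale for this one. The study is descriptive ("No sample size calculation was done as there are no statistical hypotheses in this study"), and no readable objective is to test rescue of non-responders. This stands: the point is an improvement to the analysis, not an error in a stated one.
- **Redaction.** SAP 3.4.4 and the exploratory parts of the protocol cannot be read, and infectivity is not among the readable primary or secondary endpoints. A split may already be planned there. This stands.
- **Other outputs.** Age subgroups, titer quartiles and the maximum are planned. These help little. Age is not dose-1 take; with about 10% of children positive the upper quartile is still a value below detection; and the maximum is one child's titer, not linked to dose-1 status. SAP 3.4.3.1 also plans titer ratios relative to pre-vaccination, and the D57 sample is labelled as pre-dose-2, so a D85/D57 ratio may be produced. The infectivity definition nevertheless names D01.
- **Small strata.** About 6 missed children at 88% take cannot settle the matter: 5/6 has an interval of 36–100%. This stands and limits the use to description.

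A reader might also infer that Protocol 4.2 and 4.3 are compatible only if few children were missed. The documents do not support that. Protocol 4.2 expects seropositive children to shed less, and shedding is analysed on the SafAS, which does not exclude RSV-exposed children. Many dose-1 misses could be exposed children who shed little after either dose. A plain yes/no split would mix them with truly missed children, so serostatus is needed too.

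**Conclusion.** The concern holds in a limited form. In the readable text, D64/D71 shedding is not conditioned on dose-1 take. At an assumed 88% take, 50–83% detection in six missed children contributes only 6–10% of the arm, and the arm shows up to 18% if about 10% of responders also shed. Separately, the D01 reference lets dose-1 antibody count as dose-2 infectivity: 40–80% with no dose-2 take in missed children, if 80% seroresponded and 50–100% of those stay above the threshold at D85. Every take, shedding and persistence rate for this trial is an assumption.

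Three stronger readings are not supported. One is that both dose-2 figures are averaged down to something low and reassuring; that fits shedding only, since infectivity is inflated. Another is that the trial cannot say whether dose 2 infected missed children; with complete data a count follows by subtraction. The third is that the missing split by itself decides the dose-2 transmission risk; transmission is measured directly in placebo recipients at D64 and D71 as a secondary endpoint.

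This is a low-severity point, worth making because the remedy is cheap.

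**What to change.** 1. **SAP 3.4.2.2.** For the RSVt arm, add a descriptive table of detected shedding, quantified shedding and titer at D64 and D71 by infectivity after vaccination 1 (yes/no), cross-classified by baseline RSV serostatus (SAP 4.2.6.3). Show counts with exact intervals.
2. **SAP 4.2.3.** Beside the D01-based version, report post-dose-2 infectivity as detection at D64/D71 and/or a rise of at least 4-fold from D57 to D85, by study group. Keep both, because a 4-fold rise is harder to reach from a high D57 titer. The placebo row shows the background from wild-type RSV.
3. **Reporting.** Comment on the expectation of lower dose-2 shedding for the dose-1 negative stratum as well as the whole arm, and say that the strata are descriptive.

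If the redacted sections already contain the split, a cross-reference is enough.

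Cost: no new samples or visits. Dose-1 infectivity and serostatus are already derived; the D57-based rise is a new variable computed from titers already planned. The downside is small cells: about 6 missed children at 88% take, fewer once crossed with serostatus, and none if every child takes dose 1.

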4.4 End of Study Definition

A participant is considered to have completed the study if he/she has completed the last visit or contact planned in the SoA.

The end of the study is defined as the date of the last visit or contact of the last participant in the study.

However, for periodic safety reports, the study is considered completed when the clinical study report is finalized.

5 Study Population

Prospective approval of protocol deviations to recruitment and enrollment criteria, also known as protocol waivers or exemptions, is not permitted.

5.1 Inclusion Criteria

5.1.1 Inclusion Criteria

Participants are eligible for the study only if all of the following criteria are met:

AGE

I01. Aged 6 months to < 24 months on the day of inclusion¹

TYPE OF PARTICIPANT AND DISEASE CHARACTERISTICS

I02. Participants who are healthy as determined by medical evaluation including medical history.

I03. Born at full term of pregnancy (≥ 37 weeks) or born after a gestation period of 27 through 36 weeks and medically stable as assessed by the investigator, based on the following definition: “Medically stable” refers to the condition of premature infants who do not require significant medical support or ongoing management for debilitating disease and who have demonstrated a clinical course of sustained recovery by the time they receive the first dose of study intervention

I04. Attends a daycare facility at least 3 days per week and 4 hours per day at which the participant would be in a contact group/playroom of at least one other child 6 to < 24 months of age who will participate in this study or is a member of a household, which includes at least one other child 6 to < 24 months of age who will participate in this study

INFORMED CONSENT

I05. Informed consent form has been signed and dated by the parent(s) or other legally acceptable representative (and by an independent witness if required by local regulations)

OTHER INCLUSIONS

I06. Participant and parent/legally acceptable representative are able to attend all scheduled visits and to comply with all study procedures

¹ “6 months to < 24 months” means from the day of the 6 months after birth to the day before the 2nd birthday

5.2 Exclusion Criteria

Pediatric participants are not eligible for the study if any of the following criteria are met:

MEDICAL CONDITIONS

- E01.** Known or suspected congenital or acquired immunodeficiency; or receipt of immunosuppressive therapy, such as anti-cancer chemotherapy or radiation therapy, within the preceding 6 months; or long-term systemic corticosteroid therapy (prednisone or equivalent for more than 2 consecutive weeks within the past 3 months)
- E02.** Known systemic hypersensitivity to any of the study intervention components, or history of a life-threatening reaction to the study intervention used in the study or to a product containing any of the same substances²
- E03.** Chronic illness that, in the opinion of the investigator, is at a stage where it might interfere with study conduct or completion³
- E04.** Any acute febrile illness in the past 48 hours that according to investigator judgment is significant enough to interfere with successful inoculation on the day of vaccination. A prospective participant should not be included in the study until the condition has resolved or the febrile event has subsided.
- E05.** Probable or confirmed ongoing case of COVID-19 at the time of enrollment
- E06.** Member of a household that contains an immunocompromised individual, including, but not limited to:
 - a person who is HIV infected
 - a person who has received chemotherapy within the 12 months prior to study enrollment
 - a person who has received (within the past 6 months) or is receiving (at the time of enrollment) immunosuppressant agents
 - a person living with a solid organ or bone marrow transplant
- E07.** Member of a household that includes, or will include, an infant who is less than 6 months of age at the time of enrollment

² The components of study intervention are listed in Section 6.1 of the protocol and in the Investigator's Brochure.

³ Chronic illness may include, but is not limited to, cardiac disorders, lung disease (including any history of reactive airway disease, receipt of bronchodilator or inhaled steroid therapy, or medically diagnosed wheezing), atopy, renal disorders, auto-immune disorders, diabetes, psychomotor diseases, and known congenital or genetic diseases

E08. Attends a daycare facility and shares a daycare room with infants less than 6 months of age, and parent/legally acceptable representative is unable or unwilling to suspend attendance at the daycare facility for 28 days following study intervention administration

E09. Any need of supplemental oxygen therapy in a home or hospital setting at the time of enrollment.

PRIOR/CONCOMITANT THERAPY

E10. Participant's mother previous receipt or planned administration of an investigational RSV vaccine or any monoclonal antibody (such as Infliximab) during pregnancy and/or breastfeeding.

E11. Receipt or planned receipt of any of the following vaccines prior to or after the first study intervention administration:

- any influenza vaccine within 7 days prior to and after, or
- any COVID-19 or inactivated vaccine or live-attenuated rotavirus vaccine within 14 days prior to and after, or
- any live vaccine, other than rotavirus vaccine, within 28 days prior to and after

E12. Previous receipt of an investigational RSV vaccine or receiving any anti-RSV product (such as ribavirin or RSV IG or RSV monoclonal antibody) at the time of enrollment.

E13. Receipt of immune globulins, blood or blood-derived products in the past 3 months

E14. Receipt of intranasal and intra-ocular medications within 3 days prior to study enrollment

E15. Receipt at the time of enrollment or previous receipt of salicylate (aspirin) or salicylate-containing products

PRIOR/CONCURRENT CLINICAL STUDY EXPERIENCE

E16. Participation at the time of study enrollment (or in the 6 weeks preceding the first study intervention administration) or planned participation during the present study period in another clinical study investigating a vaccine, drug, medical device, or medical procedure

OTHER EXCLUSIONS

E17. Deprived of freedom in an emergency setting, or hospitalized involuntarily

E18. Identified as a natural or adopted child of the Investigator or employee with direct involvement in the proposed study

If the participant has a primary physician who is not the investigator, the site should contact this physician with the participant's consent to inform him / her of the participant's participation in the study. In addition, the site should ask this primary physician to verify exclusion criteria relating to previous therapies, such as receipt of blood products or previous vaccines.

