1.3 Schedule of Activities (SoA)

Table 1.1: Schedule of activities for pediatric participants

Phase II Study, 11 Planned Visits, 2 Vaccinations, 3 Blood Samples, 9 Planned Nasal Swabs, One 6-Month Safety Follow-up Phone Call, approximately 8 Months' Duration Per Pediatric Participant

Visit/Contact*	Collection of information in the CRF	V01	V02	V03	V04	V05	V06	V07	V08	V09	V10	V11	Safety follow-up phone call	Illness Visit**
Study timelines days (D)		D01	D04	D08	D11	D15	D18	D22	D57	D64	D71	D85	D237	
Visit Interval			V01 + 3d	V01 + 7d	V01 + 10d	V01 + 14d	V01 + 17d	V01 + 21d	V01 + 56d	V08 + 7d	V08 + 14d	V08 + 28d	V08 + 6 months	
Time windows (days)		NA	[+1]	[+1]	[+1]	[+1]	[+1]	[+1]	[+7]	[+1]	[+1]	[+7]	[+14]	
Visit procedures:														
Informed consent	X	X												
Inclusion/exclusion criteria	X	X												
Collection of demographic data	X													
Collection of medical history	X Significant Medical History	X												
Physical examination	X	X							X					
Vital signs†	X	X							X					
Rapid COVID-19 test	X	X							X					

Visit/Contact*	Collection of information in the CRF	V01	V02	V03	V04	V05	V06	V07	V08	V09	V10	V11	Safety follow-up phone call	Illness Visit**
Study timelines days (D)		D01	D04	D08	D11	D15	D18	D22	D57	D64	D71	D85	D237	
Visit Interval			V01 + 3d	V01 + 7d	V01 + 10d	V01 + 14d	V01 + 17d	V01 + 21d	V01 + 56d	V08 + 7d	V08 + 14d	V08 + 28d	V08 + 6 months	
Time windows (days)		NA	[+1]	[+1]	[+1]	[+1]	[+1]	[+1]	[+7]	[+1]	[+1]	[+7]	[+14]	
Collection of reportable concomitant medications/vaccinations	X								X					X
Randomization/allocation of participant number	X	X												
Dose number	X	X							X					
Blood sampling (BL) [5 mL]	X	BL0001 Pre-vac1							BL0002 Pre-vac2			BL0003		
Nasal swab (NS)‡	X	NS0001 Pre-vac1	NS0002	NS0003	NS0004	NS0005	NS0006	NS0007		NS0008	NS0009			UN0001 to UN000X
Vaccination (vac)	X	VAC1							VAC2					
Immediate surveillance (30 min)§	X	X							X					
DC provided**		DC1							DC2					
DC reviewed††			DC1	DC1	DC1	DC1	DC1	DC1	DC1	DC2	DC2	DC2		
DC collected									DC1			DC2		
MA provided												MA		
MA reviewed												MA		
Collection of solicited administration site and systemic reactions	X	From D01 to D22							From D57 to D78					
Collection of unsolicited AEs	X	From D01 to D29							From D57 to D85					

Visit/Contact*	Collection of information in the CRF	V01	V02	V03	V04	V05	V06	V07	V08	V09	V10	V11	Safety follow-up phone call	Illness Visit†‡

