7.1 Discontinuation of Study Intervention

7.1.1 Temporary Contraindications

Should a participant experience one of the conditions listed below, the investigator will postpone further vaccination until the condition is resolved. Postponement must still be within the timeframe for vaccination indicated in the SoA.

If the postponement occurs out of the timeframe for vaccination, the participant will be permanently discontinued from study intervention but will continue to be followed for safety

TCI01: Any acute febrile illness in the past 48 hours that according to investigator judgment is significant enough to interfere with successful inoculation on the day of vaccination. A prospective participant should not be included in the study until the condition has resolved or the febrile event has subsided

TCI02: Receipt or planned receipt of any of the following vaccines prior to or after the first study intervention administration:

- any influenza vaccine within 7 days prior to and after, or
- any COVID-19 or inactivated vaccine or live-attenuated rotavirus vaccine within 14 days prior to and after, or
- any live vaccine, other than rotavirus vaccine, within 28 days prior to and after

Temporary intervention discontinuation may be considered by the investigator because of suspected AEs. For all temporary intervention discontinuations, duration should be recorded by the investigator in the source documents.

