7.1.2 Definitive Contraindications

Participants will permanently discontinue (definitive discontinuation) study intervention for the reasons listed below. These participants must not receive any additional dose of study intervention but should continue to be followed for safety and immunogenicity.

Should a participant experience at least one of the conditions listed below, the investigator will discontinue vaccination:

DCI01: An anaphylactic or other significant allergic reaction to the previous dose of vaccine

DCI02: Probable or confirmed ongoing case of COVID-19 at the time of enrollment

DCI03: Serious AE assessed as related to the study vaccine following the previous dose of vaccine, based on Investigator's judgment

In the event of a local or national immunization program with a pandemic influenza vaccine or any other vaccine as needed, participants who receive pandemic influenza vaccine or any other vaccine as needed at any time during the study will not be withdrawn from the study.

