7.1.3 Other Reasons

A participant may discontinue from study intervention at any time at his/her own parent/LAR request, or at the discretion of the investigator for safety, behavioral, or compliance reasons.

Participants should continue to be followed for safety.

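### The rules for the second live-virus dose carry forward neither the immunocompromised-household exclusion (E06) nor the child's own immunosuppression (E01), and eligibility is checked only at V01

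*Protocol*

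**What the plan says.** At entry the protocol is strict. E06 in Section 5.2 excludes a "Member of a household that contains an immunocompromised individual, including, but not limited to" people with HIV, recent chemotherapy, immunosuppressant treatment or a transplant. The treatment items are dated to entry, for example "a person who has received (within the past 6 months) or is receiving (at the time of enrollment) immunosuppressant agents". E01 excludes a child with immunodeficiency, recent immunosuppressive therapy or long-term systemic corticosteroids. E07 excludes a "Member of a household that includes, or will include, an infant who is less than 6 months of age at the time of enrollment". Section 5 rules out exceptions at this stage: "Prospective approval of protocol deviations to recruitment and enrollment criteria, also known as protocol waivers or exemptions, is not permitted".

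The row "Inclusion/exclusion criteria" in Table 1.1 is marked at V01 only, as is medical history. The second administration is at V08.

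Sections 7.1.1 and 7.1.2 list what stops or postpones that dose. Two of the items keep their entry wording: "TCI02: Receipt or planned receipt of any of the following vaccines prior to or after the first study intervention administration" and "DCI02: Probable or confirmed ongoing case of COVID-19 at the time of enrollment". Section 5.3, on lifestyle, states that nothing is required beyond the exclusion criteria and the contraindications to later vaccinations.

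**The concern.** E06 keeps shed live virus away from the household contacts most likely to be harmed by it, people who receive no study vaccine and gain no direct benefit. E01 protects the child. Both matter whenever live virus is given, and here it is given twice. A condition that is an absolute bar on D01 has no counterpart rule at dose 2, and the protocol gives no reason for the difference.

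The protocol does not treat the second dose as free of exposure for contacts. It swabs placebo children at D64 and D71 as a secondary transmission endpoint, and it enrolls close contacts with acute respiratory illness for 28 days after any administration. Yet for the most vulnerable household members it relies on a check made about two months earlier.

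**Working it through.** The check is mainly a comparison of texts, with a little arithmetic on timing and scale.

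**1. The dose-2 rules against the entry exclusions** (Sections 7.1.1, 7.1.2 and 5.2).

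| Rule for dose 2 | Subject | Matching entry exclusion |
|---|---|---|
| TCI01 | Acute febrile illness | E04 |
| TCI02 | Other vaccines | E11 |
| DCI01 | Significant allergic reaction to the previous dose | None directly (E02 in part) |
| DCI02 | COVID-19 | E05 |
| DCI03 | Vaccine-related SAE after the previous dose | None |

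Three of the five repeat entry exclusions and two concern reactions to the previous dose. None corresponds to E06, E01 or E07. No redaction appears in these sections that could hide such a rule. Restating E04, E11 and E05 would be unnecessary if entry exclusions carried forward by themselves.

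**2. What V08 would detect** (Table 1.1; Sections 6.8 and 8.2.2). Before dose 2 the site performs a physical examination, vital signs and a rapid COVID-19 test, and collects reportable medications. All concern the child. They may reveal an E01 change, but they cannot reveal a change in another household member. For E01, Section 6.8 makes immunosuppressants and systemic steroids reportable but does not prohibit them, so a detected change still triggers no mandatory action.

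**3. Age of the household check at dosing** (Table 1.1). V08 is V01 + 56 days with a window of +7 days, so the interval runs from 56 to 56 + 7 = 63 days.

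**4. Scale at dose 2.** Section 4.3 says that, across earlier attenuated candidates, the main effect of a repeat dose was infection of those who had not responded to the first. As an assumption, apply the Phase I rates for the same construct in Section 2.2 to the 50 RSVt children:
- Uninfected by dose 1, at 100% infectivity: 50 × (1 − 1.00) = 0.
- Uninfected by dose 1, at 88% infectivity: 50 × (1 − 0.88) = 6.
- Without a 4-fold neutralizing rise, at 80% responding: 50 × (1 − 0.80) = 10.

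The last figure counts antibody non-responders. In the study that gave the 80%, every vaccinee was infected, so these 10 should not be read as uninfected. The Phase I children were seronegative and received another formulation and delivery. Children here are unscreened, and Section 4.2 expects seropositive children to shed less. None of these figures counts affected households.

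**5. E07.** A birth by day 63 (63/7 = 9 weeks) at an assumed term of 37–40 weeks implies 37 − 9 = 28 to 40 − 9 = 31 weeks' gestation at D01. At 27–36 weeks it implies 27 − 9 = 18 to 36 − 9 = 27 weeks. These pregnancies would generally be known at entry, and E07 already extends to a future infant. Only an infant who joins the household unexpectedly is uncovered.

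**The case against.** The strongest reply is that the protocol has other safeguards. Section 8 directs sites to raise immediate safety concerns with the Sponsor, to decide whether dosing continues; a known immunocompromised household member is an obvious case. Section 7.1.3 adds: "A participant may discontinue from study intervention at any time at his/her own parent/LAR request, or at the discretion of the investigator", and safety is one of the permitted grounds. Section 5.5 allows a temporary delay, and the internal safety committee (Section 10.1.5) may recommend a pause in vaccination. Staff meet the parent at V02 to V08, so a change that is mentioned can be acted on. Much new immunodeficiency or cancer in the child would surface through SAE reporting within 24 hours. Contacts with acute respiratory illness should be seen and swabbed. Section 4.2 expects lower shedding after dose 2, and Section 4.3 describes a generally high level of restriction of repeat doses.

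These points narrow the risk and most of them stand. The gap for E01 is smaller than for E06, and the gap for E07 is smaller still. But these safeguards permit withholding case by case, or detect exposure afterwards. None prompts a household question before dose 2, and none makes withholding mandatory. The consent pages and Investigator's Brochure are not in view, so nothing is claimed about what parents are told to report or what further guidance sites hold.

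**Conclusion.** The concern holds. A site following the written rules exactly could give live virus at dose 2 to a child whose household would have barred entry at D01. E06 is the main gap: neither detection nor withholding is required. For E01 detection is plausible, but withholding is still not mandated.

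The likely size is small and cannot be quantified. Harm would need shedding after dose 2 to coincide with a new E06 condition that was not acted on, and the documents give no rate for such conditions. The non-responder counts rest on Phase I rates carrying over to a different formulation and an unscreened population. The change is worth making because the people exposed are vulnerable and the remedy is cheap, not because many events are expected. Confidence is medium.

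**What to change.** - Add to Section 7.1 contraindications mirroring E06 and E01, and E07 for an infant who joins the household unexpectedly, each dated to the day of the second administration. The sponsor should decide whether each is temporary or definitive.
- Add to Table 1.1, at V08 before dosing, a short household and immune-status re-check.
- Apply both to all pediatric participants regardless of arm, so that the blind is kept, with follow-up continuing as Section 7.1 provides.

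The cost is a few questions at an existing visit and possibly a few second doses not given. That would mean slightly fewer dosed children contributing at D64 and D71 (shedding and secondary transmission) and at D85 (immunogenicity). The re-check cannot catch household changes that arise after dosing.
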